12.5. Procedures to be Followed in the Event of Abnormal Laboratory Test Values

In the event of unexplained abnormal laboratory test values, the tests should be repeated immediately and followed up until they have returned to the normal range and/or an adequate explanation of the abnormality is found. Abnormal laboratory values or test results constitute AEs only if they induce clinical signs or symptoms, are considered clinically significant, or require therapy. For abnormal laboratory test values related to AEs of special interest refer to [Section 12.4](#).

12.6. Clinical Laboratory Parameters and Abnormal Laboratory Test Results

Clinically significant changes, in the judgment of the Investigator, in laboratory parameters (abnormalities) will be recorded as AEs.

During the treatment period, all Total WBC and WBC differential results will be blinded. If any of the following results are observed, the Investigator will be notified and asked to repeat the laboratory tests:

- Absolute lymphocyte count [ALC] < 200 cells/ μ L
- Absolute neutrophil count [ANC] < 1000 cells/ μ L
- Total WBC > 20,000 cells/ μ L

If the repeat values also exceed these limits, the Investigator will be informed that the patient's results for the abnormal parameter have fallen outside the acceptable thresholds.

If ANC or total WBC counts are confirmed outside the acceptable limits, the Medical Monitor will contact the treating investigator to request close monitoring for risk of infection and appropriate follow-up, at the discretion of the investigator.

If ALC results are confirmed as below 200 cells/ μ L, the investigator will be instructed that study drug is to be temporarily discontinued. Laboratory testing will be repeated weekly until the results have returned to within the following acceptable ranges:

- ALC > 500 cells/ μ L

When values have returned to acceptable values, the Investigator will be informed that the values are no longer outside of the acceptable range and that study drug may be restarted. (See [Section 9.5.1](#) instructions on resuming treatment after dose interruptions.)

12.7. Abnormal Clinical Safety Findings

Clinically significant changes, in the judgment of the Investigator will be recorded as AEs.

12.8. Treatment of Overdose of Study Medication

An overdose is any dose of study treatment given to a patient or taken by a patient that exceeds the dose described in the protocol. There is no information regarding overdose with RPC1063. Any overdose, with or without associated AEs, must be promptly reported to [REDACTED] Drug Safety Center. Overdoses do not need to be recorded as AEs in the eCRF; only in case of any AEs associated with the overdose, these should be reported on relevant AE/SAE sections in the eCRF.

12.9. Procedures in Case of Pregnancy

Pregnancy in itself is not regarded as an AE unless there is a suspicion that an investigational product may have interfered with the effectiveness of a contraceptive medication. However, the outcome of all pregnancies (spontaneous miscarriage, elective termination, normal birth or congenital abnormality) must be followed up and documented even if the patient was discontinued from the study.

Male patients should also be instructed to notify the treating investigator in the event that their female partner becomes pregnant. Attempts should be made to follow female partners of study patients, if they should become pregnant. The treating investigator must obtain informed consent from the pregnant partner of a study patient prior to collecting data on her pregnancy and its outcome.

All reports of congenital abnormalities/birth defects are SAEs. Spontaneous miscarriages should also be reported and handled as SAEs. Elective abortions without complications should not be handled as AEs. All outcomes of pregnancy must be reported to [REDACTED].

13. PLANNED STATISTICAL METHODS

13.1. General Considerations

All patients will be randomized to either placebo (Part A) or IFN β -1a (Part B), RPC1063 0.5 mg, or RPC1063 1 mg in a 1:1:1 ratio, stratified by the following factors:

- EDSS at Baseline (≤ 3.5 , >3.5)
- Country

All efficacy and safety data will be listed by patient. Baseline is defined as the last observed measurement prior to the Day 1 receipt of randomized study medication.

Descriptive statistics will consist of the number of patients (n), mean, standard deviation (SD), median, minimum, and maximum for continuous variables and counts and percentages for categorical variables.

All analyses using [REDACTED] or higher.

13.2. Sample Size Estimation

Part A

The primary analyses [REDACTED] will compare the cumulative number of new GdE lesions at the end of Week 24 in each of the RPC1063 groups to the placebo group using a 2-sided Wilcoxon-Mann-Whitney test. For this type of nonparametric analysis, the parameter of interest for sample size/power considerations is the probability that a randomly selected patient in an active treatment arm will have fewer lesions than a randomly selected patient in the placebo arm. Limited data are available from which to estimate this parameter. However, based on the use of patient-level data from [Tubridy et al. \(1999\)](#) and [Miller et al. \(2003\)](#), estimates of this probability range from 0.634 to 0.754. Using the approach of [Noether \(1987\)](#), a sample size of 59 patients per group will provide 80% power to detect a difference if the true value of this probability is equal to 0.65 ([Noether, 1987](#)). Assuming a dropout rate of 15%, the planned enrollment is 210 patients (70 patients per arm).

Part B

Approximately 1200 patients with RMS will be randomized in this part of the study (approximately 400 per treatment group). The primary analyses will compare the ARR in each of the RPC1063 groups to the IFN β -1a group using a Poisson regression model at the $\alpha = 0.025$ level. The control ARR is assumed to be equal to 0.3 ([Mikol, 2008](#)). Assuming extra-Poisson variation ($\sigma^2=1.3$) ([Polman, 2011](#)) and 24 months of follow-up per patient, a total sample size of 999 patients (333 per arm) is estimated to provide 90% power to detect a 37% reduction in the ARR (i.e., an ARR of 0.19 for RPC1063) ([Nicholas, 2011](#)). In order to account for an assumed dropout rate of 17%, approximately 1200 patients (400 per arm) will be enrolled.

13.3. Statistical Analysis Plan

A Statistical Analysis Plan (SAP) will be written and finalized prior to any lock of the study database. The SAP will provide a detailed description of the statistical methods and expand on the details provided in the protocol. Additional analyses may be added. Tables, listing and figures shells will also be provided.

13.4. Randomization

Patients will be randomized into the study on Day 1 using an IVRS provided by .

Part A

- Patients will be randomized 1:1:1 to receive placebo, 0.5 mg RPC1063, or 1 mg RPC1063. The randomization will be stratified by country.

Part B

- Patients will be randomized 1:1:1 to receive IFN β -1a 30 μ g, 0.5 mg RPC1063, or 1 mg RPC1063. The randomization will be stratified by baseline EDSS (≤ 3.5 , > 3.5) and country.

Treatment groups are described in [Section 9.5.1](#).

13.5. Analysis Populations

The following analysis populations will be used in the statistical analysis:

Intent-to-Treat (ITT): The ITT population will consist of all randomized patients who received at least 1 dose of study medication, with treatment assignment designated according to randomized treatment.

In Parts A and B, the primary efficacy analysis will be carried out in the intent-to-treat population.

Per Protocol (PP): The PP population will consist of the subset of the ITT population that excludes those patients who have had a major protocol violation. These will be defined prospectively, in advance of data lock and primary analyses, in the final SAP, by the (aggregate results blinded) project statistician. Membership in the PP population will be determined prior to unblinding.

Safety: The Safety population will consist of all patients receiving any study treatment and safety analyses will be carried out on this population according to highest dose of RPC1063 (up to 1 mg) actually received.

13.6. Statistical Methods

13.6.1. Missing Data

Part A

Last observation carried forward (LOCF) and mean imputation will be used for patients with missing post-baseline lesions. If a patient is missing at most 2 post-baseline scans, then the last non-missing, post-baseline observation will be carried forward to impute the missing value.

However, if there are no values to be carried forward or if the patient is missing more than 2 scans, then the mean number of lesions from patients in the same treatment group at the same visit will be used as the imputed value. Sensitivity analyses will be specified in the SAP.

Part B

Sensitivity analyses will be specified in the SAP.

13.6.2. Demographic and Baseline Data

Demographic and baseline data will be summarized by treatment group and frequency distributions and summary statistics presented.

13.6.3. Patient Disposition

Patient disposition will be summarized and summary statistics presented.

13.6.4. Efficacy

Part A

For the primary analysis, the cumulative number of GdE lesions from Week 12 to Week 24 will be compared between the 1 mg RPC1063 group and the placebo group using the stratified Wilcoxon-Mann-Whitney test, stratified by presence of GdE lesions at baseline (absent or present). This comparison will be assessed using a 2-sided test at the $\alpha=0.04944$ level of significance (to keep the overall Part A level of significant at $\alpha=0.05$, accounting for the O'Brien-Fleming adjustment and interim analysis) (Reboussin, 2000). If the comparison between the 1 mg RPC1063 group and placebo is statistically significant, then a second primary analysis will similarly compare the 0.5 mg RPC1063 group and the placebo group, also based on a 2-sided test at the $\alpha=0.04944$ level of significance. Sensitivity and descriptive analyses will also be presented.

The secondary endpoint of the proportion of patients free of GdE lesions at Week 24 will be analyzed using a logistic regression model with treatment group (three levels) and presence of baseline GdE lesions (absent, present) as factors. Pairwise comparisons between the 1 mg RPC1063 group and placebo, and between the 0.5 mg RPC1063 group and placebo, will be tested.

Quantitative endpoints such as the percent brain volume change over 24 weeks will be analyzed using analysis of covariance models with treatment group as a factor and the baseline value of the corresponding parameter as a covariate.

Endpoints that are defined in terms of lesion counts will be analyzed using the Wilcoxon-Mann-Whitney test. These analyses will include only the two groups being compared.

All secondary endpoints will be analyzed using 2-sided tests at the 5% level of significance.

Part B

The primary analysis for the ARR will be carried out using a Poisson regression model. The model will compare treatment groups, adjusted for region, age, and the number of GdE lesions at baseline. To account for multiple comparisons, each of the 2 treatment comparisons with IFN β -1a will be tested at the $\alpha = 0.025$ level. Results will be summarized by randomized treatment group and expressed as unadjusted and adjusted relapse rates, odds ratios, corresponding 95% confidence intervals, and p-values.

The relapse rate will be based on only those relapses that were determined by the treating investigator to meet the protocol-defined definition of relapse, based on the EDSS scores obtained by the blinded evaluator (Section 9.1.2.3). New or recurrent neurological symptoms that occur less than 30 days following the onset of a protocol-defined relapse will be considered part of the same relapse, i.e., if 2 relapses have onset days that are ≤ 30 days of one another, they will be counted as 1 relapse (see Section 9.1.2.3).

The relapse rate for each treatment group will be calculated as:

$$(\text{total relapses in the arm}) / (\text{total days in the study for the arm}) * 365.25$$

The 3 key secondary endpoints will be tested in order in [redacted] ranking the RPC1063 1 mg dose above the RPC1063 0.5 mg dose. If both doses are significant on the primary endpoint, then the first comparison on the key secondary endpoints will be between the RPC1063 1 mg group and the IFN β -1a group at the 5% level of significance. If that comparison is successful, then the same endpoint will be tested for the RPC1063 0.5 mg group vs. the IFN β -1a group comparison at the 5% level of significance. This procedure will continue down the key secondary endpoint list until a comparison fails to reach statistical significance, [redacted]. If only 1 RPC1063 dose is significant on the primary endpoint, then the [redacted] will be employed on the surviving dose only, at the 2.5% level of significance for each key secondary endpoint.

The key secondary endpoints of cumulative number of new or enlarging T2 lesions between baseline and Month 12 and the number of GdE lesions at Month 12 will be analyzed using a negative binomial regression model with factors for treatment, region, age, and baseline number of GdE lesions. The key secondary endpoint of time to onset of disability progression will be compared between treatment groups using Kaplan-Meier estimation and a Cox proportional-hazards model adjusted for region, age, and baseline EDSS score. Results will be summarized by randomized treatment group and expressed as proportions, corresponding 95% confidence intervals, and p-values. Disability progressions confirmed at 3 months and at 6 months will be analyzed separately.

Other secondary endpoints that are defined as continuous variables will be analyzed using analysis of covariance models adjusted for region, age, and baseline measurements of the response parameter of interest. Other secondary endpoints defined as response proportions will be analyzed using a Cochran-Mantel-Haenszel test stratified by region and baseline EDSS category.

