For a nonparametric analysis using the Wilcoxon-Mann-Whitney test, the parameter of interest for sample size/power considerations is the probability that a randomly selected patient in an active treatment arm will have fewer lesions than a randomly selected patient in the placebo arm. Although limited data are available from which to estimate this parameter, estimates of this probability range from 0.634 to 0.754 (Tubridy, 1999; Miller, 2003). Using the approach of Noether (1987), a sample size of 59 patients per group will provide 80% power to detect a difference if the true value of this probability is equal to 0.65 (Noether, 1987). Assuming a dropout rate of 15%, the planned enrollment is 210 patients (70 patients per arm).

Part B:

The primary analysis of ARR during the active treatment period will be carried out using a Poisson regression model which will include factors for treatment groups, region, age, and number of GdE lesions at baseline. To account for multiple comparisons, each of the two RPC1063 treatment group comparisons with the IFN β -1a group will be tested at the $\alpha = 0.025$ level. Results will be expressed as unadjusted and adjusted relapse rates, odds ratios, corresponding 95% confidence intervals, and p-values.

The 3 key secondary endpoints will be tested in order in a ranking the RPC1063 1 mg dose above the RPC1063 0.5 mg dose. If both doses are significant on the primary endpoint, then the first comparison on the key secondary endpoints will be between the RPC1063 1 mg group and the IFN β -1a group at the 5% level of significance. If that comparison is successful, then the same endpoint will be tested for the RPC1063 0.5 mg group vs. the IFN β -1a group comparison at the 5% level of significance. This procedure will continue down the key secondary endpoint list until a comparison fails to reach statistical significance. If only 1 RPC1063 dose is significant on the primary endpoint, then the will be employed on the surviving dose only, at the 2.5% level of significance for each key secondary endpoint.

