### 2 Introduction

RPC01-201 is a phase 2/3 clinical trial consisting of a placebo-controlled (Part A, Phase 2) and active comparator trial (Part B, Phase 3) versus IFN  $\beta$ -1a [REDACTED] in patients with relapsing multiple sclerosis (RMS). Part A is a randomized, double-blind comparison of RPC1063 to a placebo control in patients with RMS to characterize the short-term efficacy and safety of RMS in improving disease activity as measured by MRI parameters. Part B characterizes the efficacy and safety profile of RPC1063 on longer-term clinical outcomes (e.g., relapse rate and disability progression) in RMS patients.

This statistical analysis plan (SAP) describes the statistical methods to be used during the reporting and analysis of clinical data collected in Part A of the study. This plan should be read in conjunction with the study protocol and the case report forms (CRFs).

Analyses of data collected during the optional extension of Part A, as well as analysis of data collected during Part B of the study will be described in separate SAPs. A separate analysis plan will also be developed to guide analyses of population pharmacokinetic (PK) data and a separate analysis plan will be developed to guide analyses of heart rate data collected from the Holter monitors.

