#### *Analysis method – annualized relapse rate*

## 16.1.9 Documentation of Statistical Methods

Receptos, Inc.  
Protocol RPC01-201

Statistical Analysis Plan – Part A, V1.2  
Date Issued: May 20, 2014

ARR at the end of Week 24 will be analyzed using a Poisson regression model. The model will compare treatment groups, adjusted for region, the number of relapses within 24 months prior to the study, and presence of GdE lesions. A sensitivity analysis will be using a negative binomial regression model to compare ARR with the same covariates as specified for the Poisson model.

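### The Part B primary relapse-rate test is called a Poisson regression with no variance estimator, yet the trial is sized for variance 1.3 times Poisson; with plain Poisson variance at that dispersion, type I error is about 0.049 per dose, not 0.025

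*Protocol*

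**What the plan says.** Protocol section 13.6.4 (Part B) states: "The primary analysis for the ARR will be carried out using a Poisson regression model". The model adjusts for region, age and number of baseline GdE lesions, and each dose is compared with interferon at 0.025. The synopsis agrees: "The primary analysis of ARR during the active treatment period will be carried out using a Poisson regression model". Neither place mentions a scale parameter, robust standard errors or a negative binomial model for this endpoint.

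Section 13.2 sizes the same test with "Assuming extra-Poisson variation" of 1.3 and concludes that "a total sample size of 999 patients (333 per arm) is estimated to provide 90% power to detect a 37% reduction in the ARR".

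Further detail is deferred. Protocol section 13.3 says "The SAP will provide a detailed description of the statistical methods and expand on the details provided in the protocol", and section 2 of the SAP supplied, which covers Part A, says "analysis of data collected during Part B of the study will be described in separate SAPs". For the Part A relapse rate, SAP section 9.2.1 says "ARR at the end of Week 24 will be analyzed using a Poisson regression model", again with no scale; negative binomial regression appears there only as a sensitivity analysis. For the Part B lesion counts, by contrast, protocol section 13.6.4 names negative binomial regression explicitly.

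**The concern.** A Poisson regression run with its default variance takes the variance of the counts to equal their mean. The plan expects the variance to be 1.3 times the mean. Under that expectation the default standard error is too small by a factor of sqrt(1.3) = 1.14, and the test rejects too often.

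This is the confirmatory comparison with the active control. Under section 13.6.4 it also decides whether the key secondary endpoints are tested, for which doses and at what level, so an inflated error rate carries down the hierarchy. Leaving the variance unstated also leaves a choice that could be made after the data are seen.

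**Working it through.** **Inputs (protocol 13.2).** Control rate 0.30 per year, RPC1063 rate 0.19, 24 months of follow-up, dispersion 1.3 (read as variance = 1.3 x mean), alpha 0.025 per dose, power 90%. The Part B text does not state sidedness; two-sided is assumed because it is the reading that reproduces 333.

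Derived values: 24-month means 0.60 and 0.38; V = 1/0.60 + 1/0.38 = 4.298; d = ln(0.38/0.60) = -0.4568, so d^2 = 0.2086; z(0.0125) = 2.2414; z(0.10) = 1.2816.

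**Step 1: reproduce 333 per arm** (Wald test on the log rate ratio).

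- Standard error scaled by 1.3: n = (2.2414 + 1.2816)^2 x 1.3 x 4.298 / 0.2086 = 332.4, so **333**, the stated figure.
- No dispersion anywhere: the same formula without 1.3 gives 255.7, so 256.
- Plain Poisson test on data with dispersion 1.3: n = (2.2414 + 1.2816 x sqrt(1.3))^2 x 4.298 / 0.2086 = 282.4, so 283.

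Other readings:

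- One-sided 0.025 with the factor gives 282.
- Using 0.189 (37% unrounded) gives 326, and a rate-difference form gives 327. Both are close, and both still need the 1.3.
- A negative binomial with shape 1.3 gives 402 to 410 at alpha 0.025. It comes near 333 only at alpha 0.05 (341 with 0.189), which contradicts the stated level.

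**Step 2: type I error with plain Poisson variance.** If the true residual dispersion is s, the test statistic has standard deviation sqrt(s) under the null, so the per-dose error is 2 x (1 - Phi(2.2414/sqrt(s))). At s = 1.3, 2.2414/1.140 = 1.966, which gives 0.0493. The familywise figures treat the two comparisons as correlated 0.5 through the shared control arm. The documents give no dispersion after covariate adjustment, so values other than 1.3 are an assumed range.

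| s | Per dose | Familywise |
|---|---|---|
| 1.0 | 0.0250 | 0.0465 |
| 1.1 | 0.0326 | 0.0601 |
| 1.2 | 0.0407 | 0.0745 |
| 1.3 (plan) | 0.0493 | 0.0896 |
| 1.4 | 0.0582 | 0.1049 |
| 1.5 | 0.0672 | 0.1205 |

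**Step 3: simulation under the null.** Gamma-Poisson counts, three arms of 400, 17% dropout spread evenly over 24 months, no covariates, 20,000 runs per dispersion value.

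| s | Plain | Pearson-scaled | Robust |
|---|---|---|---|
| 1.1 | 0.0314 | 0.0244 | 0.0245 |
| 1.2 | 0.0397 | 0.0260 | 0.0259 |
| 1.3 | 0.0485 | 0.0268 | 0.0266 |
| 1.4 | 0.0554 | 0.0255 | 0.0248 |
| 1.5 | 0.0655 | 0.0254 | 0.0253 |

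Simulated familywise error at 1.3 is 0.0876 for the plain test; across all five values it is 0.0453 to 0.0495 for the scaled test and 0.0454 to 0.0494 for the robust test. A separate simulation with full follow-up (400,000 trials) gave 0.048 to 0.049 per dose for the plain test at 1.3, with 333 or 400 per arm.

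**Step 4: power after the fix, at 333 per arm.** Scaled Poisson: Phi(0.4568/sqrt(1.3 x 4.298/333) - 2.2414) = 0.9005. For a negative binomial test, SE^2 = (V + 2k)/333 with k = 0.3/m, where m is the 24-month mean at which the variance is 1.3 times the mean:

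| m | k | Power |
|---|---|---|
| 0.60 (control) | 0.500 | 91.6% |
| 0.49 (average) | 0.612 | 90.4% |
| 0.38 (active) | 0.789 | 88.4% |

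**The case against.** The strongest reply is that the document meant to hold this detail is not available. The protocol assigns methodological detail to the SAP, and Part B has its own. One can say that the protocol omits the variance estimator, but not that it was never prespecified. The sizing also points towards a scaled test: the sponsor anticipated overdispersion and enrolled patients to cover it. And the figure of 0.049 needs both an unscaled test and a residual dispersion of 1.3, although region, age and baseline GdE lesions may absorb part of that.

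All of this stands as a limit on the claim. It shows that inflation is possible, not that it will occur. It does not remove the gap. The protocol fixes the model, the covariates and the alpha but leaves out the one element on which that alpha depends. The plain reading is a natural one, because the same section names negative binomial regression for the lesion counts and does not do so for relapses. The Part A SAP gives no reassurance, though it concerns a different part of the study and carries limited weight. Partial absorption by covariates reduces the inflation without removing it: at 1.1 the error is still 0.033 per dose.

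**Conclusion.** The concern holds. The protocol names a model whose default variance contradicts its own planning assumption, and its sample size implies a correction that the analysis text does not state. If the plain variance is used and residual dispersion is 1.3, the per-dose error is 0.049, about twice the stated 0.025, and the familywise error is about 0.090 against 0.046.

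This rests on a two-sided test, on reading 1.3 as a variance-to-mean ratio, and on no correction being made in the Part B SAP. If that SAP already specifies a scaled or robust variance, only the protocol wording needs aligning. Because the primary test's error rate depends on the answer, it must be settled before unblinding.

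**What to change.** In section 13.6.4, the synopsis and the Part B SAP, state that the primary test is a Poisson regression with Pearson-scaled (or robust) standard errors and log follow-up time as offset. The offset makes the model estimate the relapses-per-time rate that section 13.6.4 defines. State that the test is two-sided. This is about one sentence in each place, and the sample size stays as it is, since the scaled test delivers the stated 90% power.

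A negative binomial regression is an acceptable alternative, with power between 88.4% and 91.6% as shown above.

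A minor correction in the same passages: the synopsis says "Results will be expressed as unadjusted and adjusted relapse rates, odds ratios", and section 13.6.4 does likewise. A Poisson model estimates rate ratios, so the term should be replaced.

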9.4.1. Inclusion Criteria

To be eligible to participate in this study, candidates must meet the following inclusion criteria:

1. MS, as diagnosed by the revised 2010 McDonald criteria
2. Exhibiting a relapsing clinical course consistent with RMS and history of brain MRI lesions consistent with MS
3. Ages 18-55 years, inclusive

4. EDSS score between 0 and 5.0 at baseline
5. Meet one of the following disease activity criteria:
 - a. At least 1 documented relapse within the last 12 months prior to screeningOR
 - b. At least 1 documented relapse occurred within the last 24 months prior to screening and evidence of at least 1 GdE lesion on brain MRI within the last 12 months prior to randomization
6. No history of relapse with from 30 days prior to screening until randomization; during this period, patients must have been clinically stable, without systemic corticosteroid treatment or adrenocorticotrophic hormone (ACTH)
7. Ability to provide written informed consent and to be compliant with the schedule of protocol assessments
8. Patients of reproduction potential (males and females) must practice an acceptable method of birth control (acceptable methods of birth control in this study include: surgical sterilization, intrauterine devices, oral contraceptive, contraceptive patch, long acting injectable contraceptive, vasectomy, or double-barrier method [condom or diaphragm with spermicide OR condom and diaphragm]) during study participation and for 30 days after their last dose of treatment of study medication or true sexual abstinence (periodic abstinence [calendar, symptothermal, post-ovulation methods] and withdrawal are not acceptable methods of contraception)
9. Patients must have documentation of positive Varicella Zoster virus (VZV) IgG antibody status or complete VZV vaccination at least 30 days prior to study entry

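### The Part B primary relapse-rate model omits the EDSS randomisation stratum and the prior relapse count, at a small cost in efficiency

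*Protocol*

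**What the plan says.** Part B randomises 1:1:1 within strata of EDSS (cut at 3.5) and country. Protocol 13.4: "The randomization will be stratified by baseline EDSS". The primary relapse-rate model is given in Protocol 13.6.4, "The model will compare treatment groups, adjusted for region, age, and the number of GdE lesions at baseline", and in the Synopsis as "a Poisson regression model which will include factors for treatment groups, region, age, and number of GdE lesions at baseline".

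EDSS does enter other Part B analyses in Protocol 13.6.4. The tests of response proportions are "stratified by region and baseline EDSS category", and disability progression uses a "hazards model adjusted for region, age, and baseline EDSS score".

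For Part A, SAP 9.2.1 adjusts the Week 24 relapse-rate model for region, "the number of relapses within 24 months prior to the study, and presence of GdE lesions".

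Sample size (Protocol 13.2) is worked out "Assuming extra-Poisson variation" of 1.3. The SAP supplied covers Part A only; SAP section 2 defers Part B to a separate plan, and Protocol 13.3 says the SAP will elaborate on the protocol's methods.

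**The concern.** Two baseline variables that the sponsor uses elsewhere are missing from the analysis that decides Part B. One defines the randomisation strata. The other is past relapse frequency, which the sponsor's own Part A model treats as a covariate for the same kind of outcome. The documents give no reason for leaving out either.

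What is at stake is precision. A prognostic covariate left out of a count model stays in the residual variation. A stratification factor left out means that the standard error takes no credit for balance the design has already secured.

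**Working it through.** **Inputs.** From Protocol 13.2: control rate 0.30 and RPC1063 rate 0.19 per year, 24 months of follow-up, dispersion 1.3, level 0.025 per comparison. Expected relapses per patient are 0.30 × 2 = 0.60 and 0.19 × 2 = 0.38. The true log rate ratio is ln(0.19/0.30) = −0.45676.

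**1. The plan's own figure.**
- n = 1.3 × (2.2414 + 1.2816)² × (1/0.60 + 1/0.38) / 0.45676² = 332.4, so 333 per arm, as stated.
- SE at 333 = √[(1.3/333) × 4.298] = 0.1295.
- Power = Φ(0.45676/0.12954 − 2.2414) = 0.9005.

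This needs 0.025 two-sided; one-sided gives 282. No credit is taken for covariates, so the 90% does not depend on the change proposed here.

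**2. Bias.** With randomised allocation and a log link, omitting a balanced prognostic covariate does not move the rate ratio. This was simulated with 400 per arm, 1,500 trials per setting and 17% non-informative dropout. Assumed rate ratios were 1.3 per prior relapse with 1.5 for EDSS above 3.5, then 1.5 with 2.0.
- Both covariates omitted: mean log rate ratio −0.453 and −0.459 against −0.457 (Monte Carlo SE 0.003).
- Type I error with an estimated scale: 0.026 and 0.023 against 0.025.
- Dropout made to depend on both arm and prior relapses: −0.452 and −0.441, a slight attenuation.

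**3. Prior relapse count.** The documents give no prognostic strength. Assume a 60/30/10% split over three levels and a rate ratio of 1.2 to 1.6 per step.
- Squared coefficient of variation of the rate: 1.23936/1.104² − 1 = 0.0169 at 1.2; 2.02336/1.336² − 1 = 0.1336 at 1.6.
- Share of the variance of the log rate ratio: 2 × CV² / (1.3 × 4.298) = 0.6% to 4.8%.
- In patients per arm: 2.0 to 15.9 at 333, or 2.4 to 19.1 at 400.
- If half of this overlaps with GdE count: 0.3% to 2.4%.
- Power at 333 with this covariate alone: 90.2% to 91.5%; with half overlap, 90.15% to 90.78%.

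**4. Both covariates, simulated.** 333 per arm, 20,000 trials per setting, EDSS exactly balanced, dispersion 1.3 before adjustment, scale estimated. The low end takes 15% above EDSS 3.5 with rate ratio 1.3, and 1.2 per relapse step. The top end takes 25% with 1.8, and 1.6 per step.

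| Setting | Quantity | Base | + EDSS | + relapses | Both |
|---|---|---|---|---|---|
| Low | Sampling SD | 0.1302 | 0.1302 | 0.1300 | 0.1300 |
| Low | Scaled SE | 0.1298 | 0.1295 | 0.1295 | 0.1292 |
| Low | Power (%) | 90.9 | 91.0 | 91.0 | 91.1 |
| Top | Sampling SD | 0.1284 | 0.1284 | 0.1252 | 0.1249 |
| Top | Scaled SE | 0.1298 | 0.1274 | 0.1263 | 0.1242 |
| Top | Power (%) | 91.2 | 91.8 | 92.4 | 92.9 |

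Adding EDSS alone does not change the sampling SD; only the estimated SE moves. The gain from both is 91.1 − 90.9 = 0.2 points and 92.9 − 91.2 = 1.7 points. The lower figure is about one Monte Carlo standard error of a single power estimate, √(0.91 × 0.09/20,000) = 0.002. Type I error under the null is 0.023 without the covariates and 0.023-0.025 with both.

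**5. If the Poisson scale were fixed at 1.** The actual level is 2 × [1 − Φ(2.2414/√1.3)] = 0.049 against a nominal 0.025. Simulated levels are 0.049 and 0.042 without the covariates, and 0.048 and 0.037 with both. The covariates do not cure this.

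**The case against.** The case for leaving the model alone is substantial.

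- A covariate list need not mirror the stratification factors, and nothing in the protocol says it will. This stands: the protocol breaks no rule of its own.
- The Part A model serves a secondary endpoint over 24 weeks. It uses presence rather than number of GdE lesions and has no age term. Different covariates for a different design are not a contradiction. This also stands; Part A shows only that the sponsor regards prior relapses as a covariate for relapse rate.
- The Part B SAP was not supplied and may already add these terms. That limits the point to the model the protocol states, but does not change that model.
- The sizes come from assumed strengths. A stronger assumption (rate ratio 1.5 per relapse, SD of 1.0 relapses) lowers the dispersion by 0.0876, or 0.0876/1.3 = 6.7%. Protocol 13.2 also does not say whether 1.3 is before or after covariate adjustment.

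Three stronger readings are tempting, and the documents do not support them. A reader might infer that omitting a stratification factor biases the primary comparison; step 2 shows that it does not, apart from the slight attenuation when dropout depends jointly on arm and prior relapses. A reader might credit both covariates as true variance reductions, which in closed form takes power at 333 from 90.1% to 92.4%. That counts EDSS as reducing a variance that balanced allocation has already reduced; the simulated gain is the fair figure. A reader might also blame the omissions for an inflated test level. That arises only if the scale is fixed at 1, which Protocol 13.6.4 does not say and which sits badly with the 1.3 in Protocol 13.2.

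**Conclusion.** The omissions are real and worth correcting, but they are a missed efficiency and not a flaw in validity. The absence of bias and of type I error inflation rests on two conditions: dropout is not jointly related to arm and prior relapses, and overdispersion is estimated. On those conditions the planned 90% power stands without the change.

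The benefit is at most modest, and the two covariates act differently. EDSS corrects a slightly conservative standard error, and only when the scale is estimated. The prior relapse count gives a true but small reduction in variance. All sizes take 1.3 as the dispersion before adjustment. This is a point to consider, justified mainly by how little it costs.

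**What to change.** Before Part B unblinding, in the Part B SAP or by amendment:

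- Add EDSS category, as randomised, to the primary relapse-rate model. It is known for every randomised patient.
- Add the number of relapses in the 24 months before screening, if the Part B eCRF holds it. Check this first: eligibility asks only for a minimum (Protocol 9.4.1, "At least 1 documented relapse occurred within the last 24 months prior to screening", or one relapse within 12 months), although SAP 7.2.2 summarises a count for Part A. If no count exists, adding EDSS alone still aligns the model with the randomisation and corrects the scaled standard error.

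The cost is two model degrees of freedom and one eCRF check. Specifying the terms in advance matters, because covariates added after unblinding would be open to challenge.

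As a separate matter, not part of the gain above: Protocol 13.6.4 names only a Poisson model. One sentence should state that overdispersion is estimated (scaled Poisson, negative binomial or robust variance), in line with the 1.3 used for sizing. With a scale fixed at 1, the actual level would be about 0.04-0.05 instead of 0.025.
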